7.1.2.2 Sensitivity analysis

Same analysis will be performed on ITT population with imputation of values in case of missing data with LOCF technique (baseline value or value in case of withdrawal) and without imputation (observed cases).

In case of conclusion of non-inferiority of DM05 compared to Optive®, the superiority of DM05 compared to Optive® will be tested. The superiority analysis carried out on the ITTT population will be considered as the main analysis. Results will be also provided on the PP population.

7.1.3 Secondary endpoint(s)

Quantitative data:

Quantitative variables will be summarized by number of patients, mean, median, standard deviation, minimum, and maximum for each time point. Changes from baseline will also be calculated and tabulated for each time-point (D35-D0 and D84-D0).

A mixed ANOVA model (PROC MIXED) for repeated measures will be fitted to raw data, including the factor treatment as fixed (2 levels), time as fixed (3 levels), and product by time interaction, as well as the patient effect as random.

From this model, the contrasts of interest will be built on the adjusted means:

- * to test whether each change from baseline (D35-D0 and D84-D0) differ significantly from 0 by product.
- * to test whether the products differ significantly for each change from baseline (D35-D0 and

D84-D0).

The underlying assumptions (normality and homoscedasticity) will be checked using Shapiro-Wilk test and graphical representations of the residuals. In case of strong deviation, a non-parametric approach will be performed.

Qualitative data:

Categorical variables will be summarized with frequency and percentages for each time point.

For the global performance, treatments groups will be compared with a Chi2 test.

For other qualitative variables, the changes from baseline for each product will be assessed with a Wilcoxon signed-rank test. The comparison between the treatments will be assessed with a Mann-Whitney test for each change from baseline (D35-D0 and D84-D0).

Safety data:

The safety data will be summarised using descriptive statistics by treatment group in the Safety population.

Summary safety assessments include AEs, best-corrected visual acuity, ocular symptoms and the global tolerance assessment by the investigator.

The adverse events will be coded using the MedDRA dictionary. The evaluation of the adverse events only considers the treatment-emergent AEs (TEAEs) with onset date on or after the day of the first study drug instillation.

The ocular TEAEs and the non-ocular TEAEs will be analysed separately.

The number and percentage of patients experiencing at least one AE will be provided by treatment group, by primary SOC and PT, for the following categories of events:

- All AEs
- All TEAEs
- Maximum severity for all events by PT (regardless of causality)
- Treatment-related AEs
- Serious AEs
- AEs that lead to study withdrawal.

The difference between treatments groups on the incidence rate will be analyzed for each PT using Fisher's exact test.

The statistical significance level of 5% will be applied for the safety analyses.

- The best-corrected visual acuity will be described in the worse eye and in the contralateral eye, at each visit and change from baseline.
- The usual severity and the usual duration of each ocular symptom upon instillation will be described at each D35 and D84 visits.
- The global tolerance assessment by the investigator will be described at each D35 and D84 visits.

7.2 SAMPLE SIZE AND ITS STATISTICAL JUSTIFICATION

The primary objective of this study is to confirm the non-inferiority of DM05 in comparison with Optive™ reference for global ocular staining assessed with a 0-15 score (Oxford score). The clinical non-inferiority margin was set at 2 points on the Oxford score. Assessing a standard-deviation equal to 2.5, a total of 68 patients (34 patients in each group) is required to reach a power of 90% to set-up the non-inferiority based on a bilateral confidence interval at 95%.

Assuming a drop-out rate of 15%, 80 patients will be randomized in the study to keep sufficient power for main analysis of the primary end point (analysis on PP population).

7.3 LEVEL OF SIGNIFICANCE AND POWER OF THE CLINICAL INVESTIGATION

All statistical tests will be assessed at $\alpha = 5\%$ level of significance in a bilateral approach.

7.4 STATISTICAL PASS/FAIL CRITERIA TO BE APPLIED TO THE RESULTS OF THE CLINICAL INVESTIGATION

Non-inferiority of DM05 versus Optive with a non-inferiority margin set at 2 points on the Oxford score.

7.5 PROVISION FOR AN INTERIM ANALYSIS, WHERE APPLICABLE

No interim analysis is foreseen.

7.6 CRITERIA FOR THE TERMINATION OF THE CLINICAL INVESTIGATION ON STATISTICAL GROUNDS

As no intermediary statistical analysis has been planned, no statistical criteria for the termination of the clinical investigation has been defined.

7.7 PROCEDURES FOR REPORTING ANY DEVIATION(S) FROM THE ORIGINAL STATISTICAL PLAN

Any modification to the statistical analysis plan due to a substantial modification of the CIP will be documented as an amendment and will be described in the final study report if applicable.

7.8 SPECIFICATION OF SUBGROUPS FOR ANALYSIS

Not applicable.

7.9 PROCEDURES THAT TAKE INTO ACCOUNT ALL THE DATA

Three populations will be defined:

- Intention to treat (ITT) population corresponding to all patients randomized
- Safety population corresponding to all patients randomized and having received at least one dose of treatment
- Per protocol (PP) population corresponding to patients of the safety population who will not present major protocol deviation (decided by the Data Review Committee during a blind review process).

7.10 TREATMENT OF MISSING, UNSUED OR SPURIOUS DATA, INCLUDING DROP-OUTS AND WITHDRAWALS

In the case of missing values, the last observation carried forward (LOCF) method will be applied using at each visit the last observation available for analysis on FAS and PP.

7.11 EXCLUSION METHOD OF PARTICULAR INFORMATION FROM THE TESTING OF THE HYPOTHESIS, IF RELEVANT

Not applicable.

7.12 IN MULTICENTRE INVESTIGATIONS, MINIMUM AND MAXIMUM NUMBER OF SUBJECTS TO BE INCLUDED BY EACH CENTRE

The recruitment will be competitive between the different centers. No minimum and maximum number of patients will be set for each center.

8- DATA MANAGEMENT

8.1 PROCEDURES USED FOR DATA REVIEW, DATABASE CLEANING AND ISSUING/RESOLVING DATA QUERIES

8.1.1 Identification of source data

All clinical data in the CIP and collected by the Investigator will be notified in the source document. OSDI questionnaire and daily log completed by the subjects will be considered as source documents.

8.1.2 Case report Form completion

e-CRFs will be used for this study. The investigator is responsible for ensuring that data are properly recorded on each subject's eCRFs and related documents. An investigator who has signed the protocol signature page or his/her authorized designee is to personally sign the eCRFs (as indicated on the eCRF) to

validate that the observations and findings are recorded on the eCRFs correctly and completely. The data reported on the eCRFs shall be derived from source documents and be consistent with these source documents, and any discrepancies shall be explained in writing. Any change or correction to data reported on an eCRF shall be dated, initialed, and explained, if necessary, and shall not obscure the original entry (ie, an audit trail shall be maintained); this applies to both written and electronic changes or corrections.

8.1.3 Data management and review

8.1.3.1 Data management

Data management will consist in the different following steps:

- Redaction of a data management plan and a data validation plan.
- Redaction of e-CRF specifications and completion guidelines for the investigators
- Redaction of annotated CRF
- Programming and validation of consistency controls
- Data Clarifications Forms (DCFs) emission and database correction
- Data listings emission
- MedDRA coding of AE/ADE and WhoDrug for concomitant medications and validation of the coding by an expert
- Data Management report

8.1.3.2 Data Review

A blind data review will be organised at DERMSCAN – PharmaScan, [name] – FRANCE or by phone.

Will be present a minima the sponsor, DermScan project manager, the statistician and the study monitor. Study coordinating investigator may be present by phone.

The study review will aim at determining the analysis population by:

- reviewing the conditions of study's realisation,
- determining the populations for the statistical analyses,
- specifying all the protocol's deviations as major or minor,
- reviewing the statistical analysis plan.

Following the study review, the statistical analysis populations will be defined and a report will be written and validated by DERMSCAN and the Sponsor. The data base will thus be corrected and locked.

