2.4 TRACEABILITY OF THE INVESTIGATIONAL DEVICE

Each product will be assigned a batch number to insure its traceability from its production to destruction. During the study, each product will be labelled with a specific label:

The labelling of the products will be realized by DERMSCAN.

Here is presented an example of the labels which will be pasted on each product, in French language:

Primary packaging if applicable:

- Study number:
- Treatment number:
- Product name and batch number:
- Administration route:

Secondary packaging:

- Study site (name and address) :
- Principal investigator: Dr. xxxxx
- Emergency phone number :
- Study number :
- Treatment number :
- Study period :
- Administration route:
- Storage conditions :
- Expiry date :
- Product name and batch number:
- Mention: For clinical use only. External use. Keep out of reach of children

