6.5.1.3 Monitoring visits

For the duration of the study, monitoring visits may be performed by the CRA in order to check the study performance in accordance with the study CIP.

The Clinical Research Associate ensures the coherence and the veracity of the data reported in the Case Report Form compared to the source data. He/she verifies that the study is performed according to the CIP and that all documentation necessary to ensure a good follow-up of the study is present and well completed.

These visits will also serve to ensure product accountability.

During these visits, the CRA reserves the right to ask for queries resolution, directly in the document(s) concerned or with specific data clarification forms. He/she ensures the completion of the Investigator file and retrieves all documents necessary for updating the trial master file.

When applicable, the CRA may retrieve duplicate of the CRF to be sent to the data management department.

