7.1.1 Analysed population

Three populations will be defined:

- Intention to treat (ITT) population corresponding to all patients randomized
- Safety population corresponding to all patients randomized and having received at least one dose of treatment
- Per protocol (PP) population corresponding to patients of the safety population who will not present major protocol deviation (decided by the Data Review Committee during a blind review process)

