7.1.2 Primary endpoint

7.1.2.1 Main analysis

The main analysis of the main criterion will be conducted on the PP population. The hypothesis of non-inferiority of DM05 compared to Optive® will be tested by calculating the bilateral 95% CI of the difference between groups (DM05 – Optive®) of the change from baseline of global ocular staining in the worse eye on Day 35. A two-way analysis of covariance (ANCOVA) model will be constructed using main effects of treatment and baseline score as covariate. Adjusted means (least square mean and error standard of the mean) by treatment will be presented as well as an estimate of the difference between adjusted means.

A 95% two-sided confidence interval, based on the ANCOVA model, will be computed for the difference of DM05 minus Optive®.

If the upper bound is no higher than 2 points for the PP population, it will be concluded that the null hypothesis can be rejected and that DM05 is non-inferior to Optive®.

The p value of non-inferiority will be expressed taking on board the predefined margin of non-inferiority.

This analysis will be based on observed cases.

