10.4 CORRECTIVE AND PREVENTIVE ACTIONS AND PRINCIPAL INVESTIGATOR DISQUALIFICATION CRITERIA

If major deviations from an investigator are observed during monitoring, the CRA will warn the investigator of the importance to respect the CIP. An investigator who continuously violates the CIP despite CRA warnings could be excluded from the investigation after agreement of the Sponsor.

11- DEVICE ACCOUNTABILITY

The IMD should only be dispensed only under the supervision of a physician approved for the study. The Investigator (or delegate) is responsible for dispensing the study products to the patients who are randomised in the study. The study devices must not be administered to patients who are not randomised in the study.

A preprinted accountability form provided by the CRO must be kept current and must identify the subject number/the number of the IMD dispensed, and the amount of IMD dispensed to and returned by each subject at each visit, with the corresponding dates.

All IMD supplies (empty containers, as well as partly used and unused IMD) must be available for inspection at every monitoring visit. The CRA or Sponsor delegate should verify the investigational site's

Horus Pharma	CIP #15E1122	Final Version 4.0 Date: 04/09/2017	Confidential Page 36/53
--------------	--------------	---------------------------------------	----------------------------

products accountability records against record of administrated doses in the CRF. All used and non-used products will be destructed after signature of the clinical report.

12- STATEMENTS OF COMPLIANCE

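### The review called blind, which fixes the primary PP set, must include the study monitor, who on the natural reading can know each subject's arm

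*Protocol*

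**What the plan says.** **The review.** Protocol 8.1.3.2 lists the attendance: "Will be present a minima the sponsor, DermScan project manager, the statistician and the study monitor". The meeting's tasks include "determining the populations for the statistical analyses" and "specifying all the protocol's deviations as major or minor". Its report is validated by the CRO and the sponsor.

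**What rests on it.** Protocol 7.1.1 defines PP as safety-population patients without a major deviation, "decided by the Data Review Committee during a blind review process". Protocol 7.1.2.1 states: "The main analysis of the main criterion will be conducted on the PP population".

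**Who sees product.** Protocol 6.5.1.3 says of monitoring visits: "These visits will also serve to ensure product accountability". Protocol section 11 requires a form that links subject number to product dispensed and returned, to be verified by the CRA or a sponsor delegate, and adds: "All IMD supplies (empty containers, as well as partly used and unused IMD) must be available for inspection at every monitoring visit". The example label in Protocol 2.4 includes "Product name and batch number". Protocol 2.7 and 6.1.2 put both products in commercial packaging.

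**What is fixed in advance.** Protocol 10.2 excludes from PP, a priori, subjects with a major deviation, with too short a treatment duration (no threshold given) or with no evaluation of the main criterion. It then leaves all observations to discussion at the review. SAP 7.1.1 says that definitions of minor and major deviations are still to be supplied.

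**The concern.** A PP primary analysis is credible only if the people who decide exclusions do not know the arm. The plan relies on this by calling the review blind. Yet the only separation it describes, in Protocol 6.1.2, is between the evaluating investigator and the person who hands out product. Protocol 8.1.5 delays release of the codes until after database lock, but that does not undo what monitoring staff have already seen on the vials and the accountability forms.

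If someone at the table knows the arm and the grading of deviations is open to judgment, exclusions can favour one product, deliberately or not. A single remark that links a subject to a product would also unblind the others present.

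**Working it through.** **Step 1: the chain in the text.**

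- The monitor must attend (Protocol 8.1.3.2).
- The meeting grades deviations and sets the populations (Protocol 8.1.3.2), and PP is defined by that grading (Protocol 7.1.1).
- The non-inferiority conclusion is drawn on PP (Protocol 7.1.2.1; SAP 7.6.1).
- Product accountability is checked by subject at monitoring visits (Protocol 6.5.1.3 and section 11), and the packaging identifies the product (Protocol 2.4, 2.7 and 6.1.2).
- Whether the attending monitor is the person who visits the sites is not stated. Protocol 6.5 gives review of the ongoing study to the monitor, and Protocol 16.2 writes monitor and CRA as one role when code envelopes are checked. Protocol 6.5.1.1 and 6.5.1.2 allow the CRA, the monitor or both. Overlap is the natural reading but not the only one.
- No section keeps monitoring staff out of classification. SAP 5.2 gives the blinded review to a Trial Management Committee and SAP 7.1.2 to a Data Review Committee. Neither says which members are blind.

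**Step 2: the plan's own figures.** Inputs from Protocol 7.2: margin 2, SD 2.5, power 90%, two-sided 95% interval, 15% drop-out. The true difference is taken as 0.

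- Normal approximation: n per arm = 2 × 2.5² × (1.960 + 1.282)² / 2² ≈ 32.8, so 33 per arm and 66 in total.
- With the noncentral t distribution, 34 per arm gives 90.2% power. This is the stated 68.
- 68 / 0.85 = 80 randomised, as stated. The plan therefore allows for 12 losses from PP.

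**Step 3: illustrative worst case.** Suppose that the k DM05 patients with the worst change are excluded, leaving 34, and that changes are normal with SD 2.5. The mean of those left falls by 2.5 × S / 34, where S is the expected sum of the k largest of 34 + k standard normal values.

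| k | S | Shift (points) | Share of margin 2 |
|---|---|---|---|
| 1 | 2.107 | 2.5 × 2.107 / 34 = 0.155 | 7.7% |
| 2 | 3.822 | 2.5 × 3.822 / 34 = 0.281 | 14.1% |
| 3 | 5.323 | 2.5 × 5.323 / 34 = 0.391 | 19.6% |

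**Step 4: the same idea as type I error.** Assumptions: true difference at the margin of 2, SD 2.5, 40 per arm before exclusion, unadjusted t interval, the k worst DM05 patients removed and k comparator patients removed at random. Repeat simulation runs put the one-sided error at 2.5% for k = 0, 4.6% to 4.9% for k = 1, 7.3% to 7.5% for k = 2 and 10.3% to 10.8% for k = 3.

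Steps 3 and 4 are bounds under deliberate selection, not forecasts. They need someone who knows both arm and Day 35 score, and a gradable deviation in exactly those patients.

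**The case against.** The other side has five fair arguments.

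- **The monitor may not be the person who handled vials.** Protocol section 11 names the CRA or a sponsor delegate, and the label in 2.4 is an example. This stands as a limit: a reader might infer that the attendee certainly knows the arm, but the documents do not say so. Commercial packaging identifies the product whatever the study label shows, and if separate people are intended the protocol should say it.
- **Attendance is not a vote.** True: Protocol 8.1.3.2 gives nobody a vote, and the CRO and sponsor validate the report. But no decision procedure is set, and a required attendee takes part in the discussion that does the grading.
- **Major deviations are not wholly open.** Correct. Protocol 10.2 sets some exclusions, so it would be wrong to infer that nothing is prespecified. The rest is left to discussion or deferred by SAP 7.1.1.
- **There are checks.** Protocol 7.1.2.2 and SAP 7.1.2 repeat the analysis on ITT, which the grading cannot touch. SAP 7.1.1 lists all deviations, and SAP 6.4 compares PP-excluded with PP-included patients if numbers allow. Large selection could show as a gap between PP and ITT. The check is partial: the conclusion is drawn on PP, and SAP 4.1.1 makes the ITT repeat follow a positive PP result.
- **A bar on access to codes could remove everyone.** Read by organisation, it would catch the sponsor and the CRO, which both hold code envelopes (Protocol 16.2) and validate the report. This stands, so the bar should apply to individuals.

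**Conclusion.** The plan places a person who probably knows the arm in a review that it calls blind, and that review fixes the set carrying the primary conclusion. Nothing in the protocol or SAP prevents that knowledge from entering the classification. This is more than a missing detail, and it should be corrected.

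The conclusion rests on the natural, unstated reading that the attending monitor has done or seen accountability checks. A sponsor attendee who acted as the accountability delegate would raise the same problem.

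The size is a worst case: about 0.15 to 0.39 points for one to three selected DM05 exclusions, under normality and SD 2.5. Even the largest leaves about 80% of the margin. A reader might infer that PP exclusions will be, or were, steered by arm. The documents show only that this is possible, and they give no basis for how likely it is.

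**What to change.** Amend Protocol 8.1.3.2, and align SAP 5.2 and 7.1.2 with it, as follows:

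- Individuals who have verified accountability, handled product or opened a code envelope do not take part in classifying deviations or deciding PP membership. This includes the visiting CRA or monitor and any sponsor delegate in that role.
- Those individuals supply, before the meeting, a deviation listing stripped of product, batch and treatment number.
- Blinded individuals from the sponsor, project management and statistics classify from that listing. The rule applies person by person, so the sponsor and CRO can still validate the report.

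Issuing the major and minor definitions that SAP 7.1.1 promises before the review would narrow the room for judgment, whoever attends.

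The cost is a wording change, one masked listing and a check that each classifying person is blind. The small downside is that the monitor cannot comment live on individual cases and must answer masked written queries instead.

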8.1.4 Preparation and lock of the Database

The database will be locked upon resolution of all queries. A copy of the locked database will be sent to the Sponsor. A signed database lock form will be provided.

After the database will be locked, any change to the database can only be done from database correction forms approved by the Project Manager and the Sponsor. If the database will need to be corrected, lock/unlock of the database must be clearly documented by the Project Manager in the study file.

8.1.5 Data unblinding at study end

Unblinding of the assigned treatments will occur after the completion of the following steps:

1. All CRF data are entered into the computer;
2. All data clarifications, if any, are resolved;
3. Major deviations or intercurrent events, if any, are defined and identified;
4. All information necessary to analyze the data is integrated into the data base;
5. The database is formally locked.

8.2 PROCEDURES FOR VERIFICATION, VALIDATION AND SECURING OF ELECTRONIC CLINICAL DATA SYSTEMS, IF APPLICABLE

Not applicable.

8.3 PROCEDURES FOR DATA RETENTION AND SPECIFIED RETENTION PERIOD

The Sponsor must archive the CIP, documentation, approvals and all other essential documents related to the study, including certificates that satisfactory audit and inspection procedures have been carried out, for 15 years DermScan - PharmaScan will archive all documents concerning the study as detailed below:

- All documents must be archived in a secure place and treated as confidential material.
- Paper documents relating to this study are stored maximum during one year on site before to be transmitted for archiving to an approved service provider.
- Data will be archived securely as digital and paper version for 15 years from the date of dispatch of the final report's acceptance.

At the end of this period of 15 years, the study archives will be destroyed unless otherwise stipulated in writing by the Sponsor.

